3.1 Synopsis

Title:	Bioavailability Study of COQUN ORAL FORMULATION (CoQ10) administered in Healthy Adults (CoQ10-01)
Investigator:	[name]
Study center:	Consult Med Iasi, [name]
Study period:	
Overall clinical duration of the study: 5 weeks
 
Recruitment duration: 1 month
 
Treatment duration:
 
The study consists of 3 periods:
 
 1. a single-dose phase, 1 day 2. a wash-out period of 7 days 3. a multidose-dose phase of 28 days 
The total duration of the study from the start of the first treatment period to the end of study visit is 35 days (5 weeks) per subject.
 
Planned study start: June 2018
 
Planned study end: August 2018
 
Planned first subject in: July 2018
 
Planned last subject out: August 2018
 
Period per subject: 5 weeks

Study phase:	Bioavailability
Indication:	Male & Female Healthy Volunteers
Study Objective:	To evaluate the best dosage for COQUN ORAL FORMULATION in order to reach a level of plasma concentration which might assure its antioxidant effect if taken on a regular basis.
Outcome Measures:	
 - Area under the curve (microg/ml x h): ≥ 5 - Cmax: $\geq 0,8$ - Tmax: ≥ 3 - elimination half-life (t 1/2)

	Study Title	Bioavailability Study of COQUN ORAL FORMULATION (CoQ10) administered in Healthy Adults (CoQ10-01)		
	Study ID	VF-BAQ10/2018	Sponsor:	VISUFARMA SpA
	Date	March 03, 2018	Vers.	Final

Study type:	Interventional, Single-center, Single- and multi-dose Bioavailability Study of COQUN ORAL FORMULATION in Healthy Adults.		
Study description:	
The study will include 24 healthy subjects who will test the CoQ10 formulation. All 24 subjects will test a single dose of 100mg CoQ10 in 1 day to assess bioavailability, which will be followed by a one week wash-out period and then by a 4 week period of continuous administration of COQUN ORAL FORMULATION in parallel groups (1:1): patients will be divided in the continuous treatment period into two groups, one group of 12 patients with intake of 100mg OD, the other one group of 12 patients with intake of 100mg BID, in order to assess multiple-dose profile of COQUN ORAL FORMULATION.
 
Patients will have to fast the night before enrolment, for at least 10 hours.
 
Patients will be requested to fill in a short diary in the multidose phase, on a daily basis, for confirming the product correct intake, and informing on any experienced adverse event and eventual medication taken for its solving.
		
Number of subjects:	To be screened:	24	
	To be divided in 2 parallel groups (1:1):	24	
	Intention-to-treat (ITT):	This set contains all randomized subjects.	
	Per protocol (PP):	This set consists of all subjects who meet all inclusion/exclusion criteria and who do not have any major protocol deviation.	
Study population:	
Inclusion criteria:
 
 • Subject Informed consent form (ICF) is signed • M & F Aged between 35-75 years at the time of the signature of ICF • A body mass index between 20 and 29 kg/m² • Fasting the night before enrolment, for at least 10 hours • Healthy, meaning absence of any prescribed medication for a month prior to the inclusion to the study and during the study • Willing to avoid a consumption of any food supplements except vitamin D and calcium at least 2 weeks before and during the study 		

	Study Title	Bioavailability Study of COQUN ORAL FORMULATION (CoQ10) administered in Healthy Adults (CoQ10-01)		
	Study ID	VF-BAQ10/2018	Sponsor:	VISUFARMA SpA
	Date	March 03, 2018	Vers.	Final

	
 Consumption of dairy and cereal products (standardized breakfast will include low lactose dairy and bread) Willing to follow all study procedures, including attending all site visits (including sessions during which a venous line will be inserted for blood sampling), and keeping a diary for the time of multiple-dose study (to follow their compliance and palatability) 
Exclusion criteria:
 
 Intake of any prescribed medication within 2 weeks of the beginning of the study Intake of any food supplements within 2 weeks of the beginning of the study, except vitamin D and calcium Hypotension Any clinically significant history of serious digestive tract, liver, kidney, cardiovascular or hematological disease, diabetes Gastrointestinal disorders or other serious acute or chronic diseases Known lactose/gluten intolerances/ food allergies (limitation for standardization of meals) Inadequate veins (in the opinion of the investigator) or known contraindication to placement of a dedicated peripheral line for venous blood withdrawal Known drug and/or alcohol abuse Using any form of nicotine or tobacco Mental incapacity that precludes adequate understanding or cooperation Participation in another investigational study or blood donation within 3 months prior to or during this study
Sample size	The sample size for this study is not based on any power calculation. 24 subjects (12 for each arm) have been considered sufficient to obtain reliable results for the exploratory purposes of the study.
Duration of treatment:	
 single-dose phase of 1 day: 24 adult healthy subjects will be given a single dose of 100 mg of COQUN ORAL FORMULATION a wash-out period of 7 days (no treatment) a multidose-dose phase of 28 days: 12 adult healthy subjects will be given OD 100mg of COQUN ORAL FORMULATION, after dinner (group A), while the other group of 12 adult healthy subjects will be given BID a dose of 100 mg of COQUN ORAL FORMULATION, after lunch and after dinner (group B)

	Study Title	Bioavailability Study of COQUN ORAL FORMULATION (CoQ10) administered in Healthy Adults (CoQ10-01)		
	Study ID	VF-BAQ10/2018	Sponsor:	VISUFARMA SpA
	Date	March 03, 2018	Vers.	Final

Investigational Product:	Study product:	COQUN ORAL FORMULATION (Coenzyme Q10 Miniactive Retard 100mg capsules)
	Dose/dosage:	Single-dose of 100 mg Multi-dose: 100mg OD (one group) vs 100mg BID (second group)
	Administration:	Single-dose of 100 mg Multi-dose: 100mg OD (one group) vs 100mg BID (second group)
Criteria for evaluation:	Dose/dosage:	Coenzyme Q10 Miniactive Retard 100mg capsules, in a vegetable case containing 30 capsules
	Administration:	po (oral formulation)
COQUN ORAL FORMULATION level of plasma concentration:	
- single-dose phase; 24 adult healthy subjects will be given a dose of 100 mg of COQUN ORAL FORMULATION and plasma coenzyme Q10 will be measured over the next 12 hours: at 1, 2, 4, 8 and 12 hours after intake. Pharmacokinetic properties including area under the curve (AUC), maximum plasma concentration (Cmax), time to maximum plasma concentration (Tmax) and elimination half-life (t 1/2) will be measured
 
- multidose-dose phase; 12 adult healthy subjects will be given OD 100mg of COQUN ORAL FORMULATION, after dinner (group A), while the other group of 12 adult healthy subjects will be given BID a dose of 100 mg of COQUN ORAL FORMULATION, after lunch and after dinner (group B); plasma coenzyme Q10 will be measured over the next 4 weeks. Pharmacokinetic properties including area under the curve (AUC), maximum plasma concentration (Cmax), time to maximum plasma concentration (Tmax) and elimination half-life (t 1/2) will be measured.
	
Safety:	Safety will be monitored through vital signs, physical exams, clinical laboratory tests (hematology, serum chemistry), and adverse events including assessment of relationship to the IP.	

	Study Title	Bioavailability Study of COQUN ORAL FORMULATION (CoQ10) administered in Healthy Adults (CoQ10-01)			
	Study ID	VF-BAQ10/2018		Sponsor:	VISUFARMA SpA
	Date	March 03, 2018		Vers.	Final

Statistical methods:	Due to the explorative aim of the study, descriptive statistics and confidence intervals at 90% level will be provided. In particular, continuous variables will be presented as arithmetic mean values \pm standard deviation (SD) and median values with interquartile range; geometric means will be provided as well; for categorical variables absolute and percentage frequencies will be provided.			
-----------------------------	---	--	--	--

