6.2 Rationale of the Study

Many studies showed the beneficial proprieties of CoQ10 on the body and on the brain especially if taken on a daily basis, as well as its properties to ameliorate oxidative stress in ischemic retina, providing a promising therapeutic potential for ameliorating oxidative stress-mediated mitochondrial dysfunction in ischemic retinal injury and for preventing RGC apoptosis and loss in glaucoma-related models.

It is expected that supplementing regularly with Q10 will raise the Q10 blood level, but much depends on the way in which the Q10 product has been prepared and much depends on the dosage. It was demonstrated that taking 30 milligrams or 50 milligrams of Q10 daily will not raise the Q10 level as much as taking 100 mg of Q10 daily will do, while taking 100 milligrams of Q10 twice daily will yield even greater gains in Q10 blood levels.

From the literature it is known that a well-absorbed Q10 supplement should over time raise the blood level to about 2.5 micrograms per milliliter if the individual is taking a 100-milligram dosage once a day, while if taken the same Q10 supplement in a dosage of 100 milligrams twice a day, its blood level should, over time, raise the steady-state Q10 blood level to somewhere in the area of 3.5 micrograms per milliliter. But, the attainable levels will vary from individual to individual, beside depending on the product itself as formulation.

Therefore, this bioavailability study is intended to be performed in order to evaluate the best dosage for COQUN ORAL FORMULATION, with its innovative technology based on the modified release of active principles at certain time intervals, in order to reach a level of plasma concentration which might assure its antioxidant effect if taken on a regular daily basis.

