10.5 Conduct of the Study

10.5.1 Screening visit & treatment start (V1, Day -7, single dose phase)

Screening visit will be performed once the subject signed the informed consent form and the following procedures will be performed:

- subject information and informed consent
- demographic data and medical history recording
- physical examination
- vital signs (blood pressure, heart rate, temperature and respiratory rate)
- body measurements (height and weight)
- 12 lead ECG
- safety laboratory analysis
- concomitant medication recording

	Study Title	Bioavailability Study of COQUN ORAL FORMULATION (CoQ10) administered in Healthy Adults (CoQ10-01)		
	Study ID	VF-BAQ10/2018	Sponsor:	VISUFARMA SpA
	Date	March 03, 2018	Vers.	Final

- assessment of inclusion/exclusion criteria

Once the subjects are considered eligible for the study, all 24 adult healthy subjects will enter the single dose treatment phase and will be given a dose of 100 mg of COQUN ORAL FORMULATION and plasma coenzyme Q10 will be measured over the next 12 hours: at 1, 2, 4, 8 and 12 hours after intake. Pharmacokinetic properties including area under the curve (AUC), maximum plasma concentration (Cmax), time to maximum plasma concentration (Tmax) and elimination half-life (t 1/2) will be measured.

Safety parameters will be monitored during the whole day.

The subjects will be requested to fasten for at least 10 hours before IP intake; when will arrive at the study center subjects will be hospitalized for at least 12 hours for the single dose phase, therefore subjects will remain at site for around 24 hours.

At the end of this visit, if no SAE occurs, subjects will be dismissed and will be requested to return after 1 week for the second study visit and multidose phase start.

In the wash-out period subjects will have to respect the same lifestyle regimen and no medication shall be taken, if not necessary.

Subjects will be given a diary and will be requested to report any possible adverse event experienced between V1 and V2, as well as any treatment taken for treating an AE, if applicable.

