10.6.15 Meals schedule

During hospitalization (V1, day -7) a dinner will be served at around 8 o`clock in the evening. If subject will remain until next day hospitalized, on next day 1 a breakfast will be served before leaving.

Water will not be permitted 1 hour before IP intake.

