5.2 Efficacy Analysis

5.2.1 Primary Efficacy Analysis

The primary objective of this study is to evaluate the best dosage between 100mg once daily or 100mg twice daily for COQUN ORAL FORMULATION in order to reach a level of plasma concentration which might assure its antioxidant effect if taken on a regular basis.

The following pharmacokinetic properties will be evaluated:

- Area under the curve (microg/ml x h)
- C_{max}
- T_{max}
- Elimination half-life (t_{1/2})

Collected Variables

- Plasma concentration of coenzyme Q10 [CRF – Visit 2, 3, 4, 5]

	Form	Form No.	1M-DMST-011-01-A1
	Statistical Analysis Plan	Page	Page 21 of 69
		Effective Date	07/05/2018

Derived Variables

Derived variables are shown in Image 1 and are the following^[2,3]:

- AUC_t
The area under the plasma concentration curve to the last quantifiable concentration (C_t) at time t (AUC_t) will be determined by linear trapezoidal rule. The trapezoidal rule is a method used to numerically approximate the area under the concentration by time curve obtained by summing the area of all trapezoids constructed under the curve. Each trapezoid's area is obtained as:

$$\frac{(C_i + C_{i+1}) * (T_{i+1} - T_i)}{2}$$

where C_i is the concentration at time i (where i is any timepoint before the last observed timepoint T_t), C_{i+1} is the concentration at the following timepoint, T_i is the timepoint i and T_{i+1} is the following timepoint.

- C_{max}
Maximum concentration in the plasma (C_{max}) is obtained directly from the data being the highest plasma concentration value.
- T_{max}
 T_{max} is the collection time in which the maximum concentration is observed and is related to the drug absorption speed.
- $t_{\frac{1}{2}}$
The terminal half-life is defined as the time required for the plasma concentration of a drug to decrease 50% in the final stage of its elimination; this parameter is computed with the formula^[2]:

$$t_{\frac{1}{2}} = \frac{\ln 2}{\lambda_z}$$

where λ_z is the smallest elimination rate constant observed which is obtained as the ratio of clearance and volume of distribution. Clearance is calculated as the ratio of dose and AUC while volume of distribution is obtained as dose divided by concentration at time 0 that is the concentration registered after the first intake of coenzyme (in the single dose time 0 is hour 1, in the multidose phase time 0 is visit 2).

[figure not shown]

Image 1. Pharmacokinetic parameters

	Form	Form No.	1M-DMST-011-01-A1

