5.2.3 Analysis of Other Variables

An analysis of the bioavailability evaluated in the first single dose phase of the study will be performed.

The following pharmacokinetic properties will be evaluated:

- Area under the curve (microg/ml x h) ≥ 5
- C_{max} (microg/ml x h) $\geq 0,8$
- T_{max} (hours) ≥ 3
- Elimination half-life ($t_{\frac{1}{2}}$)

The plasma concentration is recorded at Visit 1 at moment 0 (before COQUN intake), hour 1, hour 2, hour 4, hour 8 and hour 12.

Collected Variables

- Plasma concentration of coenzyme Q10 [CRF – Visit 1]

Derived Variables

The parameters AUC_t , AUC_{∞} , C_{max} , T_{max} , $t_{\frac{1}{2}}$ and their computation have been described in section 5.2.1 Primary Efficacy Analysis. Please refers to the mentioned section for details.

Analysis of Primary Efficacy variable:

Descriptive statistics such as mean \pm standard deviation, median with interquartile range, minimum, maximum and coefficient of variation will be presented for the plasma concentration of coenzyme Q10 at each time point in the entire sample of subjects. 95% confidence interval will be provided as well.

An explorative analysis on gender will be performed showing descriptive statistics for plasma concentration of coenzyme Q10 divided by gender. The effect of gender will be explored by means of a mixed model for repeated measures with covariates *gender*, time and the interaction term *gender*time*.

	Form	Form No.	1M-DMST-011-01-A1
	Statistical Analysis Plan	Page	Page 28 of 69
		Effective Date	07/05/2018

Change of plasma concentration versus baseline (i.e. change versus hour 0 values) will be computed for each study visit both for the whole sample and by gender. Change will be computed in the following way:

$$\text{Change (\%)} = \frac{\text{Value at Visit X} - \text{Baseline Value}}{\text{Baseline Value}} \times 100$$

Area under the curve, maximum concentration in the plasma, time of maximum concentration and terminal half-life and half-life will be presented descriptively on the original scale.

95% confidence interval will be provided for the means of the parameters AUC_t , C_{max} and T_{max} and terminal half life in the single dose phase i.e. following a single intake of COQUN oral formulation.

A concentration by time graph will be presented for the single dose phase in order to have a graphical visualization of the pharmacokinetics properties over time.

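### Single-dose CoQ10 sampling ends at 12 h, so a modified-release profile with Tmax of 3 h or more has at most two samples after its recorded peak, and a maximum at 12 h is reported as an observed peak

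*Protocol*

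**What the plan says.** The Protocol synopsis (3.1) states that "plasma coenzyme Q10 will be measured over the next 12 hours: at 1, 2, 4, 8 and 12 hours after intake". Sections 10.3, 10.5.1 and 10.6.11 repeat those times, and 10.6.11 adds a pre-dose sample. SAP 5.2.3 uses the same grid, with concentration "recorded at Visit 1 at moment 0 (before COQUN intake), hour 1, hour 2, hour 4, hour 8 and hour 12". The next CoQ10 sample is Visit 2, seven days later, which SAP 4.4 uses as the multidose baseline.

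Protocol 7.2 and 12.7 list AUC ≥ 5, Cmax ≥ 0.8, Tmax ≥ 3 and elimination half-life as the primary variables without separating the two phases. SAP 5.2.3 applies the same targets to the single dose, with Tmax in hours, but places that analysis under other variables. Protocol 6.2 describes the product's "innovative technology based on the modified release of active principles at certain time intervals".

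In SAP 5.2.1, Tmax "is the collection time in which the maximum concentration is observed" and Cmax "is obtained directly from the data being the highest plasma concentration value". For half-life, "Clearance is calculated as the ratio of dose and AUC while volume of distribution is obtained as dose divided by concentration at time 0", where time 0 means hour 1 in the single-dose phase. SAP 5.2.3 also names AUC to infinity and refers to 5.2.1 for it, but 5.2.1 defines only AUC to the last quantifiable concentration. Neither document gives a reason for stopping at 12 h.

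**The concern.** A slow-release product is expected to peak late, and the plan sets a late peak as a target. The later the peak, the less of the profile lies inside a 12 h window, which is itself half of the 24 h once-daily interval. Two things follow. First, total exposure and elimination are least well seen in the subjects in whom the release works as intended. Second, a profile still rising at the last sample produces a Tmax of 12 h and a Cmax equal to the 12 h value, and nothing in Table 28 or Listing 25 marks these as truncated.

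The single-dose bioavailability statement is at stake. A reader of the report could take AUC as total exposure, Tmax as a located peak, and half-life as a measured elimination property. Protocol 10.8 makes further studies depend on positive results here.

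**Working it through.** There is no power or sample-size calculation to reproduce (Protocol 12.3, SAP 2.5). The check is a count, followed by an illustrative model.

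**1. Count (no assumptions).** Sampling times are 0, 1, 2, 4, 8 and 12 h, and Tmax is the time of the highest value.

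| Recorded Tmax (h) | Meets ≥ 3 h | Later samples |
|---|---|---|
| 1 | no | 4 |
| 2 | no | 3 |
| 4 | yes | 2 (8, 12 h) |
| 8 | yes | 1 (12 h) |
| 12 | yes | 0 |

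The count refers to the recorded peak. A true peak at 3 h or just before 4 h is followed by three samples, but the 4 h sample is then normally the recorded maximum, which leaves two.

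**2. What the SAP half-life is.** λz = CL/V = (dose/AUC) / (dose/C(1 h)) = C(1 h)/AUC, so t½ = ln 2 × AUC / C(1 h). No terminal slope is fitted, and no sample is singled out as belonging to the elimination phase.

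**3. Illustrative model.** The documents give no half-life, so I assume 6, 12, 24 and 36 h, one compartment, first-order absorption and no endogenous baseline.

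- C(t) ∝ ka/(ka − ke) × (e^(−ke·t) − e^(−ka·t)), with ke = ln 2 / t½.
- ka is solved from Tmax = ln(ka/ke)/(ka − ke).
- Fraction of total AUC to time T = [ka(1 − e^(−ke·T)) − ke(1 − e^(−ka·T))]/(ka − ke).

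Example: t½ = 12 h and Tmax = 4 h give ke = 0.0578 and ka = 0.671. The fraction to 12 h is [0.671 × 0.500 − 0.0578 × 1.000]/0.613 = 0.45.

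The three figures in each cell are for Tmax 4 / 6 / 8 h. The last column applies the SAP formula to trapezoidal AUC on the planned grid.

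| Assumed t½ (h) | AUC0-12, % of total | AUC0-24, % of total | SAP t½ (h) |
|---|---|---|---|
| 6 | 67 / 56 / 44 | 92 / 88 / 80 | 11.3 / 16.9 / 21.7 |
| 12 | 45 / 41 / 35 | 73 / 70 / 67 | 11.3 / 16.2 / 20.8 |
| 24 | 27 / 25 / 23 | 48 / 47 / 45 | 11.0 / 15.1 / 19.1 |
| 36 | 19 / 18 / 17 | 36 / 35 / 34 | 10.8 / 14.4 / 18.1 |

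AUC0-12 therefore covers about 17–67% of the total. At a fixed Tmax, the SAP half-life hardly moves while the true half-life changes sixfold. It follows the speed of absorption.

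**4. Late peaks.** In the same model, true peaks at 10, 12, 14 and 16 h are all recorded as Tmax = 12 h with no later sample. Observed Cmax is 96–100% of the true Cmax, so the loss is about 0–4%.

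**5. Effect of one 24 h sample.** Later samples for Tmax 4, 8 and 12 h become 3, 2 and 1. A log-linear slope through 8, 12 and 24 h, at assumed half-lives of 12–36 h, is 73–87% of the true rate if Tmax is 8 h and 28–39% if Tmax is 12 h. Single-dose samples rise from 24 × 6 = 144 to 24 × 7 = 168.

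**The case against.** The case for leaving the schedule alone has real force.

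- **The study is exploratory.** Protocol 12.6 sets no hypotheses. The primary objective compares once-daily with twice-daily intake, which the single-dose profile does not address, and the SAP treats that profile as an other variable. This stands and limits the weight of the point. It does not remove it, because Protocol 7.2 lists these parameters with numeric targets and does not exempt the single dose.
- **AUC is already defined to the last quantifiable concentration.** True, so AUC0-12 is mainly a clearer label. But the SAP also names an AUC to infinity that it never defines.
- **The model is not the trial.** CoQ10 is endogenous and the SAP subtracts no baseline, so the coverage percentages do not carry over directly to the measured AUC. This stands, and they are an illustration only.

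Some stronger readings are tempting, and the documents do not support them:

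- **That an on-target Tmax and an estimable elimination phase exclude each other.** This needs a rule of three post-peak samples that appears in neither document.
- **That the standard error of a two-point terminal slope measures the damage.** The SAP fits no such slope, so that figure describes no planned output.
- **That slow absorbers pass Tmax and fail Cmax.** The planned outputs are group summaries with no per-subject pass or fail, and the modelled Cmax loss is small.
- **That a peak exactly at 12 h is unobserved.** It is sampled. The difficulty is that it looks the same as a later one.
- **That the stay makes a 24 h sample free.** Protocol 10.5.1 says "therefore subjects will remain at site for around 24 hours", but 10.6.13 offers dinner on the evening before dosing, so those hours may include the preceding night. Section 10.6.15 is conditional: "If subject will remain until next day hospitalized, on next day 1 a breakfast will be served before leaving".

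**Conclusion.** The point holds as a limit on what the single-dose phase can report. The count of 2, 1 or 0 samples after an on-target recorded peak follows from the schedule and the SAP definition alone. So does the fact that a maximum at 12 h is reported as an observed Tmax and Cmax and enters the means and confidence intervals of Table 28.

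The main effects are on Tmax (truncated at 12 h), AUC (a partial exposure) and half-life (not supported by the window, and computed by a formula that is not a terminal half-life). The effect on Cmax is small, about 0–4% in the model. The AUC coverage of about 17–67% rests on an assumed half-life of 6–36 h, Tmax of 4–8 h, one compartment and no endogenous baseline. A reader might infer that the once-daily versus twice-daily comparison is compromised by this schedule. It is not, because that comparison uses the Visit 2 to Visit 5 data.

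**What to change.** **Recommended; wording and table layout only.**

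1. In Protocol 7.2 and 12.7 and SAP 5.2.3, name the single-dose exposure AUC0-12, and delete the undefined single-dose AUC to infinity.
2. Remove elimination half-life from the single-dose primary variables in the Protocol and from the parameters in SAP 5.2.3, Table 28 and Listing 25.
3. In Table 28, report how many subjects have their maximum at 12 h. In Listing 25, show their Tmax as ≥ 12 h and mark their Cmax as a lower bound.
4. Summarise single-dose Tmax by median and range instead of mean and confidence interval. The Table 28 template already has the median, minimum and maximum.

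The cost is a protocol wording change and a SAP revision, with no new data.

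**Optional, not required.** A CoQ10 sample at about 24 h would allow AUC0-24, which matches the once-daily interval. It costs 24 more draws and assays (144 to 168) and possibly a longer stay, and it would have to be added to the Protocol flow chart and SAP 4.3. It would help half-life only if the SAP 5.2.1 formula were replaced by a terminal slope, and even then not for peaks at 8–12 h.
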